8.3.6 BG505 SOSIP.664 gp140, 100 mcg, admixed with Alum, 500 mcg (Group 6)

For all preparation steps, use a 1 mL Luer-Lok syringe with 0.01 mL graduations and a 22-27 gauge Luer-Lok needle.

- 1. Remove one vial of TBS and one vial of Alum from the refrigerator. Resuspend Alum by inverting the vial for 30-60 seconds.
- 2. Remove one vial of BG505 SOSIP.664 gp140 from the freezer. Thaw BG505 SOSIP.664 gp140 vial by holding in gloved hand. Once thawed, maintain the vial in upright position and gently swirl or tap the vial to mix the contents. Do not invert the vial.

Preparation of the Admixed Vaccine:

- 3. Withdraw 0.2 mL of Alum and inject into an empty sterile vial (mixing vial).
- 4. Withdraw 0.7 mL TBS and inject into the mixing vial. Mix by gently swirling and inverting the vial about 5 times. Do not shake vigorously.
- 5. Withdraw 0.1 mL BG505 SOSIP.664 gp140 and add it to the mixing vial. Mix by gently swirling and inverting the vial about 5 times. Do not shake vigorously.
- 6. Withdraw 0.5 mL of the mixed preparation for study participant administration. To maintain study blind, wait 30 minutes prior to study product delivery to clinic staff. Prior to administration, gently invert the syringe to resuspend admixed product.
- 7. The admixed product is stable for 4 hours at room temperature.

PART C:

8.3.7 BG505 SOSIP.664 gp140, 100 mcg admixed with 3M-052-AF, 3 mcg and Alum, 500 mcg (Group 7)

For all preparation steps, use a 1-mL Luer-Lok syringe with 0.01-mL graduations and a 22-27 gauge Luer-Lok needle.

- Remove one vial of 3M-052-AF, one vial of TBS, and one vial of Alum from the refrigerator. Resuspend Alum by inverting the vial for 30-60 seconds.
- 2 Remove one vial of BG505 SOSIP.664 gp140 from the freezer. Thaw BG505 SOSIP.664 gp140 vial by holding in gloved hand. Once thawed, maintain the vial in upright position and gently swirl or tap the vial to mix the contents. Do not invert the vial.

Preparation of Adjuvants:

- Withdraw 0.12 mL of 3M-052-AF and inject it into an empty sterile vial (mixing vial).
- Withdraw 0.2 mL of Alum and inject into the mixing vial. Mix by gently swirling and inverting the vial about 5 times. Do not shake vigorously. Allow formulation to incubate at room temperature for 30 minutes.
- Withdraw 0.58 mL of TBS and inject into the mixing vial. Mix by gently swirling and inverting the vial about 5 times. Do not shake vigorously.

Preparation of BG505 SOSIP.664 gp140:

Withdraw 0.1 mL of BG505 SOSIP.664 gp140 and add it to the mixing vial. Mix by gently swirling and inverting the vial about 5 times. Do not shake vigorously.

Preparation of the Admixed Vaccine:

- Withdraw 0.5 mL of the mixed preparation for study participant administration. Prior to administration, gently invert the syringe to resuspend admixed product.
- 8 The admixed product is stable for 4 hours at room temperature.

8.3.8 Trimer 4571, 100 mcg admixed with 3M-052-AF, 5 mcg and Alum, 500 mcg (Group 8)

For all preparation steps, use a 1-mL Luer-Lok syringe with 0.01-mL graduations and an 18-25 gauge Luer-Lok needle.

Preparation of Adjuvants:

- 1. Remove one vial of Alum from the refrigerator and equilibrate at ambient temperature (15°C to 27°C) for a minimum of 15 minutes.
- 2. Remove one vial of 3M-052-AF from the refrigerator and equilibrate at ambient temperature (15°C to 27°C) for a minimum of 15 minutes.
- 3. Mix the vial of 3M-052-AF gently by inverting 5 times. Withdraw 0.2 mL of 3M-052-AF and inject it into an empty sterile vial (mixing vial).
- 4. Mix the vial of Alum by gently inverting 5 times.
- 5. Withdraw 0.2 mL of Alum and inject into the mixing vial.
- 6. Mix and wait for 30 minutes. During this time, proceed to Step 7.

Preparation of Trimer 4571:

- 7. During the incubation period of the mixing vial, thaw one vial of Trimer 4571 at ambient temperature (15°C to 27°C) for a minimum of 30 minutes. Vial should NOT be moved directly from the freezer to the refrigerator to thaw.
- 8. Swirl the thawed, equilibrated Trimer 4571 vial for about 30 seconds with sufficient force to mix the solution, yet avoid foaming. Do NOT shake the vial. If some white to translucent particles are observed, the vial may still be used.

9. Withdraw 0.4 mL of Trimer 4571 and add it to the mixing vial. The final volume in the mixing vial will be 0.8 mL.

Preparation of the Admixed Vaccine:

- 10. Invert mixing vial gently 5 times to mix. Withdraw 0.4 mL of the mixed preparation for study participant administration. Immediately prior to administration, gently invert the syringe 10 times to mix.
- 11. The admixed product may be stored for up to 8 hours at 2°C to 8°C and/or up to 4 hours at ambient temperature (15°C to 27°C), including dose administration time.

8.3.9 Placebo (Tris-NaCl buffer) (Placebo 1-8)

- 1. Remove one vial of TBS from the refrigerator.
- 2. For Groups 1-7, use a 1 mL Luer-Lok syringe and a 22-27 gauge needle to withdraw 0.5 mL of TBS for study participant administration. For Group 8, use a 1 mL Luer-Lok syringe and an 18-25 gauge needle to withdraw 0.4 mL of TBS for study participant administration. To maintain study blind, wait 30 minutes prior to study product delivery to clinic staff.
- 3. For Groups 1-7, the placebo is stable for 4 hours at room temperature. For Group 8, the placebo is stable for up to 8 hours at 2°C to 8°C and/or up to 4 hours at ambient temperature (15°C to 27°C), including dose administration time.

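### The single 30-minute placebo wait in Section 8.3.9 does not match the Group 8 active dose, which needs at least 45 minutes of timed preparation

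*Protocol*

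**What the plan says.** Section 8.3.9 (placebo preparation, Placebo 1-8) applies one wait to every group: "To maintain study blind, wait 30 minutes prior to study product delivery to clinic staff". The same step treats Group 8 separately in other respects: "For Group 8, use a 1 mL Luer-Lok syringe and an 18-25 gauge needle to withdraw 0.4 mL of TBS for study participant administration". The next step also gives Group 8 its own storage limits. Only the wait is common to all groups.

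Section 8.3.8 (Group 8 active dose) begins with two equilibration steps:

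- "Remove one vial of Alum from the refrigerator and equilibrate at ambient temperature (15°C to 27°C) for a minimum of 15 minutes"
- "Remove one vial of 3M-052-AF from the refrigerator and equilibrate at ambient temperature (15°C to 27°C) for a minimum of 15 minutes"

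The adjuvants are then combined: "Mix and wait for 30 minutes. During this time, proceed to Step 7". Step 7 runs in parallel (its last figure is in minutes): "During the incubation period of the mixing vial, thaw one vial of Trimer 4571 at ambient temperature (15°C to 27°C) for a minimum of 30". After the thaw comes a short mixing step: "Swirl the thawed, equilibrated Trimer 4571 vial for about 30 seconds with sufficient force to mix the solution, yet avoid foaming".

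For Groups 1-4 and 7 the active instructions contain one timed hold, worded in Section 8.3.7 as "Allow formulation to incubate at room temperature for 30 minutes", with no equilibration step. Groups 5 and 6 have no incubation, and Sections 8.3.5 and 8.3.6 each give them an explicit 30-minute wait for blinding.

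Section 6.3 keeps participants and site staff other than pharmacists blinded to vaccine versus placebo throughout the trial. Section 8.4 requires whoever gives the injection to be blinded. Section 9.3 places preparation after the pre-vaccination checks.

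**The concern.** The protocol treats delivery time as a possible threat to the blind. It sets a placebo wait for that reason and adds waits to the two active groups that would otherwise be ready early. For Group 8 the equalisation fails: the active procedure gained an equilibration stage and the placebo wait did not.

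Group assignment is blinded only in Part B (Section 6.3), and Group 8 enrols after Group 7 has filled, so site staff know who is in Group 8 and can compare like with like. An unusually early syringe could hint at placebo, and the same interval recurs at all three vaccination visits. The exposed data are site-level symptom grading and judgements of relatedness, which belong to Part C primary endpoint 1 (Section 5.3.1).

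**Working it through.** This is a sum of the timed steps that must follow one another. Handling time is left out because the protocol gives no figures for it.

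**Groups 1-7, reproducing the protocol's figure**

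- Groups 1-4 and 7: timed hold in active preparation = 30 min; placebo wait = 30 min; gap = 30 − 30 = 0.
- Groups 5 and 6: explicit wait = 30 min; placebo wait = 30 min; gap = 0.

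The 30-minute figure is therefore reproduced for these groups.

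**Group 8 active dose (Section 8.3.8)**

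- Equilibration of Alum and 3M-052-AF: at least 15 min each. They can run together, so 15 min is the shortest reading.
- Incubation 30 min and trimer thaw at least 30 min, in parallel: max(30, 30) = 30 min.
- Swirl: about 0.5 min.

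| Reading | Active, timed steps (min) | Placebo wait (min) | Gap (min) |
|---|---|---|---|
| Vials equilibrated together, no swirl | 15 + 30 = 45 | 30 | 15 |
| Vials equilibrated together, with swirl | 15 + 30 + 0.5 = 45.5 | 30 | 15.5 |
| Vials equilibrated one after the other, with swirl | 15 + 15 + 30 + 0.5 = 60.5 | 30 | 30.5 |
| Vials equilibrated before the clock starts, with swirl | 30 + 0.5 = 30.5 | 30 | 0.5 |

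The first three rows follow Section 8.3.8 from its first step. The last is an assumption about local practice that the protocol neither requires nor forbids.

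**How many participants this touches**

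- Placebo in Part C: 12 in total − 2 in Part A (1 + 1) − 8 in Part B (4 × 2) = 2.
- Vaccine in Part C: 115 − 15 − 80 = 20, which agrees with n = 10 per arm in Section 6.1.4.
- Section 8.1 defines a placebo for both Group 7 and Group 8, so one placebo recipient in Group 8 is inferred. The Group 7 and Group 8 sizes are not legible in the schema table as extracted.

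**Room for a longer wait**

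Section 8.3.9 allows Group 8 placebo up to 4 hours (240 min) at ambient temperature, and 45 < 240.

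**The case against.** The strongest reply is that Sections 8.3.8 and 8.3.9 do not strictly contradict each other. Section 8.3.9 sets a wait before delivery; it does not order release at minute 30, and a pharmacist who knows both procedures could hold the placebo longer within the storage limits. The assignment is normally known up to 4 working days before enrolment (Section 9.3), so vials could be brought to ambient temperature early, which cuts the gap to about 0.5 minute. Pharmacy guidelines and study-specific procedures, which are not part of the protocol, may address this. The match for Groups 1-7 is also only approximate, because active preparation there includes thawing and mixing that placebo does not need.

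Much of this is fair, and it makes the leak conditional. It does not rescue the instruction. Neither remedy is written down, Section 9.3 has the vaccine prepared after the checks are complete, and the syringe overlay in Section 8.3.10 hides appearance, not timing. The untimed handling in Groups 1-7 is not a prescribed 15-minute stage.

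Two stronger readings should be resisted:

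- **That delivery time identifies the placebo recipient.** A reader might infer this, but someone would have to notice about 15 minutes against ordinary pharmacy variation, in a multicentre trial where a site may see few Group 8 deliveries. The text supports only that timing may suggest the assignment.
- **That the safety review after the first five Group 8 participants, or the blinded attribution behind FDA reports, is compromised.** The first is done by the safety review team (Section 11.3.3), whose roles in Section 11.1.1 do not include receiving syringes. The second concerns the sponsor's medical officer not being routinely unblinded (Section 11.2.3). Neither is described as seeing delivery times.

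**Conclusion.** The point holds as a gap in the pharmacy instructions. For Group 8 the stated placebo wait falls short of the timed preparation of the active dose by at least 15 minutes, so followed literally it does not do the job for which it is given. The shortfall rests on two assumptions: preparation begins after the participant is cleared, and vials are not equilibrated beforehand.

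The consequence for results is small. About one placebo recipient is involved, no formal between-arm testing of adverse events is planned (Section 6.4.3.2), and the other Part C primary endpoint is a laboratory neutralization assay. Participants record symptoms in a diary, and erythema and induration are graded mainly by diameter, which narrows the exposure further. No sample-size statement or analysis changes. It is a minor correction, worth making because it is cheap.

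**What to change.** Reconcile Sections 8.3.8 and 8.3.9 on release time for Group 8, in either of two ways:

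- In step 2 of Section 8.3.9, give Group 8 placebo its own delivery wait, matched to the minimum timed preparation of the Group 8 active dose (at least 45 minutes).
- State that Group 8 vaccine and placebo are both released at the same fixed time after preparation begins.

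The second option also absorbs the variation between equilibrating the vials together and in turn. Leave Groups 1-7 and every active-preparation step unchanged.

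The cost of the first option is one sentence and about 15 more minutes at each vaccination visit for the placebo recipient, well inside the stated 4-hour ambient limit. A fixed release time costs more only if it is set later than 45 minutes.

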8.3.10 Labeling of Study Product

Label the study product as follows and apply an overlay/tape to each syringe to ensure blinding is maintained:

- Participant identifier(s)
- Study Product Name in blinded manner, for example:
 - Protein (BG505 SOSIP.664 gp140 or Trimer 4571) + Adjuvant(s) or Placebo
- Final volume (mL)
- Route (IM)
- Beyond use date and time
- Any additional information required by jurisdiction

8.4 Administration

All injections are to be given IM in the deltoid, using standard IM injection technique.

When preparing a dose in a syringe and administering the dose, consideration should be given to the volume of solution in the needle before and after the dose is administered. Particularly, if the needle used to withdraw the product is replaced prior to vaccine administration, consideration should be given to conserving the full dose of product. The pharmacy and clinic staff members are encouraged to work together to administer the dose specified in the protocol.

Any administrator of study product will be blinded to the individual participant's treatment assignment.

8.5 Acquisition of study products

BG505 SOSIP.664 gp140 and Tris-NaCl buffer were manufactured by Ajinomoto Althea, Inc (San Diego, CA, USA) and will be provided by the International AIDS Vaccine Initiative (IAVI, New York, NY, USA).

Trimer 4571 was manufactured by Leidos Biomed (Vaccine Research Center, Frederick, MD, USA) and will be provided by DAIDS, NIAID, NIH (Rockville, MD, USA).

Alum was manufactured by Leidos Biomed (Vaccine Research Center, Frederick, MD, USA) and will be provided by DAIDS, NIAID, NIH (Rockville, MD, USA).

3M-052-AF (labeled as AP 60-702) is manufactured and provided by Access to Advanced Health Institute (AAHI, Seattle, WA, USA).

GLA-LSQ (labeled as AP 10-602) was manufactured by the Access to Advanced Health Institute (AAHI) (AAHI, Seattle, WA, USA) and will be provided by DAIDS, NIAID, NIH (Rockville, MD, USA)

CpG 1018 (labeled as CpG 1018 Drug Product) was manufactured by Aji Bio-Pharma (Ajinomoto Althea, Inc., San Diego, CA, USA) and will be provided by DAIDS, NIAID, NIH (Rockville, MD, USA).

Once an HVTN CRS is protocol registered, the pharmacist can obtain study products from the NIAID Clinical Research Products Management Center (CRPMC) by following the ordering procedures outlined in Pharmacy Guidelines and Instructions for DAIDS Clinical Trials Networks.

8.6 Pharmacy records

The HVTN CRS pharmacist is required to maintain complete records of all study products. The pharmacist of record is responsible for maintaining randomization codes and randomization confirmation notices for each participant in a secure manner.

8.7 Final disposition of study products

For US clinical research sites, all unused study products must be returned to the CRPMC after the study is completed or terminated unless otherwise instructed by the study sponsor. For non-US clinical research sites, all unused study products must be destroyed after the study is completed or terminated unless otherwise instructed by the study sponsor. The procedures are included in the Pharmacy Guidelines and Instructions for DAIDS Clinical Trials Networks.

9 Clinical procedures

The schedules of clinical procedures are shown in Appendix Q, Appendix R Appendix S, and Appendix T.

9.1 Informed consent

Informed consent is the process of working with participants so that they fully understand what will and may happen to them while participating in a research study. The HVTN informed consent form documents that a participant (1) has been informed about the potential risks, benefits, and alternatives to participation, and (2) is willing to participate in an HVTN study. Informed consent encompasses all written or verbal study information HVTN CRS staff provide to the participant, before and during the trial. HVTN CRS staff will obtain informed consent of participants according to HVTN policies and procedures.

The informed consent process continues throughout the study. Key study concepts should be reviewed periodically with the participant and the review should be documented. At each study visit, HVTN CRS staff should consider reviewing the procedures and requirements for that visit and for the remaining visits. Additionally, if any new information is learned that might affect the participants' decisions to stay in the trial, this information will be shared with trial participants. If necessary, participants will be asked to sign revised informed consent forms.

An HVTN CRS may employ recruitment efforts prior to the participant consenting. For example, some HVTN CRSs use a telephone script to prescreen people before they come to the clinic for a full screening visit. Participants must sign a screening or protocol-specific consent before any procedures are performed to determine eligibility. HVTN CRSs must submit recruitment and prescreening materials to their IRB/EC and any applicable Regulatory Entity (RE) for human subjects protection review and approval.

Note: As defined in the DAIDS Protocol Registration Manual, an RE is "Any entity/body that has the power to regulate which includes authorities that review submitted clinical data and those that conduct inspections. These are sometimes referred to as competent authorities. These are entities/bodies whose approval/authorization/acknowledgment of a clinical trial is required for conducting a clinical trial. Any organization whose approval is required prior to a CRS's participation in DAIDS funded and/or Sponsored Clinical Trial. Includes but not limited to approvals from state/national health systems and administrative bodies, drug agencies etc." CRSs are responsible for knowing the requirements of their applicable REs.

9.1.1 Screening consent form

Without a general screening consent, screening for a specific study cannot take place until the site receives protocol registration from the DAIDS RSC Protocol Registration Office.

Some HVTN CRSs have approval from their IRB/EC and any applicable RE to use a general screening consent form that allows screening for an unspecified HIV vaccine trial. In this way, HVTN CRS staff can continually screen potential participants and, when needed, proceed quickly to obtain protocol-specific enrollment consent. Sites conducting general screening or prescreening approved by their IRB/EC and any applicable RE may use the results from this screening to determine eligibility for this protocol, provided the tests are conducted within the time periods specified in the eligibility criteria.

9.1.2 Protocol-specific consent forms

The protocol-specific consent forms describe the study products to be used and all aspects of protocol participation, including screening and enrollment procedures. Sample protocol-specific consent forms for Parts A, B, and C of the main study are located in Appendix A, Appendix B, and Appendix C. A separate sample consent form for other uses of specimens is located in Appendix G. An addendum consent form for participation in the Part A Optional Second Boost is located in Appendix D (Sample addendum to informed consent form for Part A with Optional Third Vaccination participants only).

Each HVTN CRS is responsible for developing a protocol-specific consent form(s) for local use, based on the sample protocol-specific consent forms in Appendix A, Appendix B, Appendix C, Appendix D and Appendix G. The consent form(s) must be developed in accordance with requirements of the following:

- CRS's IRB/EC and any applicable REs,
- CRS's institution, and
- Elements of informed consent as described in Title 45, CFR Part 46 and Title 21 CFR, Part 50, and in ICH E6, Good Clinical Practice: Consolidated Guidance 4.8.

Study sites are strongly encouraged to have their local CABs review their sitesspecific consent forms. This review should include, but should not be limited to, issues of cultural competence, local language considerations, and the level of understandability.

The sample informed consent forms include instructions for developing specific content.

Regarding protocol registration, sites should follow procedures outlined in the current version of the DAIDS Protocol Registration Manual.

9.1.3 Assessment of Understanding

Study staff are responsible for ensuring that participants fully understand the study before enrolling them. This process involves reviewing the informed consent form with the participant, allowing time for the participant to reflect on the procedures and issues presented, and answering all questions completely.

An Assessment of Understanding is used to document the participant's understanding of key concepts in this HIV vaccine trial. The participant must complete the Assessment of Understanding before enrollment. Staff may provide assistance in reading and understanding the questions and responses, if necessary. Participants must verbalize understanding of all questions answered incorrectly. This process and the participant's understanding of the key concepts should be recorded in source documentation at the site.

IRB/EC and any applicable RE may require that a participant has signed either a screening or protocol-specific consent document prior to administering the Assessment of Understanding. The consent process (including the use of the Assessment of Understanding) should be explained thoroughly to the IRB/EC and any applicable RE, whose recommendations should be followed.

9.2 Pre-enrollment procedures

Screening may occur over the course of several contacts/visits, up to and including before vaccination on day 0. All inclusion and exclusion criteria must be assessed within 56 days before enrollment, unless otherwise specified in the eligibility criteria (or below in this section).

After the appropriate informed consent has been obtained and before enrollment, the following procedures are performed:

- Medical history, documented in the case history record
- Assessment of whether the volunteer is at low risk for HIV infection (see Appendix U)
- Complete physical examination, including height, weight, vital signs, and clinical assessments of head, ears, eyes, nose, and throat; neck; lymph nodes; heart; chest; abdomen; extremities; neurological function; skin (and pelvic and/or rectal exam for volunteers agreeing to provide mucosal samples)
- Assessment of concomitant medications the volunteer is taking, including prescription and nonprescription drugs, vitamins, topical products,

alternative/complementary medicines (eg, herbal and health food supplements), recreational drugs, vaccinations, and allergy shots

- Laboratory tests, including:
 - Screening HIV test
 - HBsAg
 - Anti-HCV Abs
 - CBC with differential and platelets
 - Chemistry panel (ALT, creatinine)
 - Urine dipstick
 - Urine or serum pregnancy test (volunteers who were assigned female sex at birth); Persons who are NOT of reproductive potential due to having undergone total hysterectomy or bilateral oophorectomy (verified by medical records), are not required to undergo pregnancy testing.
- Administration of behavioral risk assessment (BRA) questionnaire
- Obtaining of volunteer demographics in compliance with the NIH Policy on Reporting Race and Ethnicity Data: Subjects in Clinical Research, Aug. 8, 2001 (available at http://grants.nih.gov/grants/guide/notice-files/NOT-OD-01-053.html)
- Counseling on HIV testing and risk reduction, performed in compliance with the US Centers for Disease Control and Prevention (CDC)'s current guidelines or other local guidelines for HIV counseling, testing, and referral as described in Section 9.7
- Discussion of pregnancy prevention. A pregnant or breastfeeding person may not be enrolled in this trial. Specific criteria and assessment of contraception and pregnancy status are described in study inclusion criteria. Discussion of pregnancy prevention includes advising a participant who was assigned female sex at birth and who reports no current sexual activity that could lead to that participant becoming pregnant to have a plan to begin adequate birth control. This plan would be put to use if, during the study, the participant becomes sexually active in a way that could lead to that participant becoming pregnant.
- Assessment of volunteer eligibility for optional procedures

